8.4.3 Key Secondary Efficacy Analysis

Change from Baseline to Week 6 in the CGI-S scores will be assessed using the same MMRM model used for the change in PANSS scores.

Each study drug dose will be compared with placebo and model-based point estimates for the treatment effects, 95% confidence intervals (CIs), and p-values will be calculated. The analysis set will be the FAS.

In order to control the family-wise Type I error rate, the Hochberg-based matched parallel gatekeeping procedure will be used to account for multiple doses and multiple primary and key secondary endpoints.

The primary and key secondary efficacy hypotheses will be grouped into 2 hierarchical families. Family 1 is the HP-3070-9.0 versus placebo (Hypothesis 1) and HP-3070-18.0 versus placebo (Hypothesis 2), based on the primary endpoint of change from baseline in PANSS total score at Week 6. Family 2 is HP-3070-9.0 versus placebo (Hypothesis 3) and HP3070-18 versus placebo (Hypothesis 4), based on the key secondary endpoint of change from Baseline in CGI-S at Week 6.

Noven Pharmaceuticals, Inc.
HP-3070-GL-04
HP-3070

72

The matched parallel gatekeeping procedure performs multiplicity adjustments as follows:

1. The comparisons for the primary endpoint (Hypotheses 1 and 2) are performed using a truncated Hochberg procedure ($\gamma = 0.9$).
2. The comparisons for CGI-S (Hypotheses 3 and 4) corresponding to the doses that were significant in Step 1 are performed, using a regular Hochberg procedure.

Further details are provided in the SAP.

8.4.4 Other Secondary Efficacy Analyses

The same statistical model will be used for the analysis for the change from Baseline in the PANSS subscales, CDSS, CGI-S, and the scores for CGI-I, and MSQ at each assessment.

The differences in proportions of CGI-I, and PANSS responders will be analyzed using the Cochran-Mantel-Haenszel Test.

Details are provided in the SAP.

8.4.5 Subgroup Analyses

Details of subgroup analyses for primary and key secondary objectives are described in the SAP.

8.4.6 Safety Analyses

Safety analyses will be performed on the Safety Analysis Set (SAF).

Scores for C-SSRS, SAS, BARS, and AIMS will be summarized for each treatment arm using descriptive statistics at each visit for raw numbers and change from baseline values.

Adverse events will be coded using MedDRA. The collection of AEs will begin after the subject has signed the ICF. The TEAEs during the double-blind treatment period are defined as AEs with onset date on or after the start of study medication through the 30 day follow-up period, or AEs with onset prior to the first dose of study medication and with an increase in severity after the start of study medication through the 30 days follow-up period. The same rule applies for Run-in Period.

For each study treatment, numbers of events and incidence rates will be tabulated by preferred term and system organ class. Adverse events will be summarized separately for the Screening/Run-in Period and Double-blind Treatment Period. Adverse events will be summarized by severity and relationship to drug. If the subject has the same AE on multiple occasions, the summary will reflect the maximum severity or closest relationship reported.

The SAEs, including death as an outcome, and AEs leading to withdrawal of subjects will be tabulated for each treatment arm. Commonly occurring AEs, i.e., those which occur in 5% or more of the subjects in any treatment arm will be summarized using descriptive statistics.

Noven Pharmaceuticals, Inc.
HP-3070-GL-04
HP-3070

73

All laboratory test results, vital signs measurements, ECG results, weight, and body mass index will be summarized for each treatment arm using descriptive statistics at each visit for raw numbers and change from baseline values.

Patch adhesion and adhesive residue assessment results will be summarized at each visit by treatment arm, and by treatment arm overall.

The results of the PK analyses will be presented in a stand-alone report.

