8.4 Statistical Methods

All analyses, summaries, and listings will be performed using SAS[®] software (Version 9.2 or higher).

Baseline characteristics, efficacy and safety data will be summarized using the appropriate descriptive statistics.

For the efficacy variables, descriptive statistics (including n, SD, mean, minimum, maximum, and 95% CI) for the changes from Baseline during the 6-week treatment period will be presented.

Continuous variables will be summarized by descriptive statistics (sample size [n], mean, SD, median, minimum, and maximum). Categorical variables will be summarized in frequency tables (n, frequencies, and percentages). Individual subject data will be presented in listings.

All statistical tests of treatment effects will be performed at a 2-sided significance level of 0.05, unless otherwise stated.

Additional details concerning statistical methods are presented in the SAP.

All references to study medication refer only to the double-blind treatment period.

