8.4.1 Analysis Populations

Four analysis sets will be used in analyzing the data obtained from this protocol:

Intent-to-Treat (ITT): includes all consented and randomized subjects. Regardless of any protocol deviations, analyses performed on the ITT set will be based on the randomized treatment assignment and all available data.

Full Analysis Set (FAS): includes all consented and randomized subjects who have had at least 1 patch of double-blind study medication applied and who have a Baseline PANSS total score and at least 1 post-Baseline assessment of the primary efficacy measure (PANSS total score). Evaluable subjects will be defined as those who meet the FAS definition. The FAS will be used as the primary set for analysis of efficacy endpoints based on randomized treatment assignment.

Safety Analysis Set (SAF): includes all subjects who have had at least 1 patch of double-blind study medication applied and who have at least 1 post-dose safety measurement during the double-blind treatment period. In the unlikely event that errors may have occurred in treatment arm assignments, then analyses using the SAF will be based on treatment actually received. The SAF will be used for the analysis of dermal evaluations and safety endpoints.

Pharmacokinetic Analysis Set (PAS): includes all subjects who have received at least 1 dose of study medication during the double blind treatment period and have at least 1 blood sample for PK assessment. Subjects may be excluded from the PAS set if they significantly violate inclusion or exclusion criteria, significantly violate the protocol in a way that may

Noven Pharmaceuticals, Inc.
HP-3070-GL-04
HP-3070

71

influence the PK analysis, if any unexpected error occurs during the study that may influence the PK analysis (e.g., early detachment of transdermal systems, apparent sample switching, etc.) or if their data are unavailable or incomplete. The PAS will be used for the analysis with model based approach. Excluded cases will be documented together with the reason for exclusion.

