8.6 Safety

Safety variables will be summarized based on the SAF.

Noven Pharmaceuticals, Inc.
HP-3070-GL-04
HP-3070

74

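### The run-in adverse-event summary rests on a set that excludes everyone who left during run-in, and its event window is contradictory

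*Protocol*

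**What the plan says.** **Which table is promised.** Protocol section 8.4.6: "Adverse events will be summarized separately for the Screening/Run-in Period and Double-blind Treatment Period".

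**Which subjects it uses.** Section 8.6 states "Safety variables will be summarized based on the SAF", and 8.4.6 opens with the same rule. Section 8.4.1 defines the SAF: it "includes all subjects who have had at least 1 patch of double-blind study medication applied and who have at least 1 post-dose safety measurement" in the double-blind period. The same section closes the list of sets: "Four analysis sets will be used in analyzing the data obtained from this protocol". These are the ITT, FAS, SAF and pharmacokinetic sets.

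**Which events it uses.** Section 8.4.6 defines double-blind treatment-emergent AEs (TEAEs) as "AEs with onset date on or after the start of study medication through the 30 day follow-up period", or earlier events that worsen in that window. It then adds "The same rule applies for Run-in Period". Section 8.4 says "All references to study medication refer only to the double-blind treatment period". Section 8.6.1 gives a shorter TEAE definition with no end date and no mention of run-in.

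**What is collected.** AEs are recorded from consent (6.2.1.1). Two placebo patches a day are worn in run-in (5.7) while prohibited medication is washed out, and anyone who leaves before randomisation is classed as a screen failure (4.1.1).

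**The concern.** A table that describes a period should count the people who were in that period and the events that happened in it. Here the population rule admits only subjects who got through run-in, and the event rule does not say where run-in stops.

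Run-in is when subjects come off their antipsychotics and first wear the patch system. Section 2.4 limits patch-specific risk to dermal reactions, 8.6.4 reports skin irritation and discomfort as TEAEs, and 6.2.1.1 makes worsening schizophrenia an AE. Someone who reacts to the patch or deteriorates during washout is a natural candidate to leave before randomisation. If those subjects are left out, run-in AE incidence is computed on run-in survivors only.

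**Working it through.** **Step 1: the population.** Membership of each set for a subject who wore single-blind patches and left before randomisation:

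- ITT: no, not randomised.
- FAS: no, not randomised and no double-blind patch.
- SAF: no, no double-blind patch.
- Pharmacokinetic set: no, it needs a double-blind dose.

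The subject is in none of the four sets. Section 8.5 summarises disposition for all enrolled subjects and characteristics for all subjects, but neither summary reports AEs. The exclusion follows from the definitions and needs no assumed rate.

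**Step 2: how many.** The protocol states no run-in loss rate, so this part is assumption. Let f be the share of subjects starting run-in patches who are not randomised, with 612 randomised (3 × 204). Omitted subjects = 612/(1 − f) − 612.

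- f = 0.10: 680 − 612 = 68
- f = 0.20: 765 − 612 = 153
- f = 0.30: 874.3 − 612 = about 262

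Under 4.1.1, patches start while screening results are still awaited, so a subject who fails on a laboratory value, on the PANSS criteria at Baseline or on patch compliance may already have been exposed.

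**Step 3: the window.** Inputs: run-in 3 to 14 days (4.1), double-blind 42 days (4.1.2), follow-up 30 days (4.1.3). Three readings can be taken from the text:

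- *A, the rule carried over whole:* from the first run-in patch through follow-up. Length 3 + 42 + 30 = 75 to 14 + 42 + 30 = 86 days, of which 72 days fall after run-in (72/75 = 96%; 72/86 = 84%). These are shares of calendar days, not of events.
- *B, study medication as 8.4 defines it:* the window starts at the first double-blind patch, so the run-in set equals the double-blind set.
- *C, the periods kept apart as 8.4.6 says:* from the first run-in patch to before the first double-blind patch, 3 to 14 days. No end is stated for subjects who are never randomised.

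**Step 4: test records, counted in the run-in table.**

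- Application-site reaction on run-in day 3, subject withdrawn: 0 under A, B and C alike, because the SAF excludes the subject.
- Insomnia on run-in day 3, resolved, subject later in the SAF: A 1, B 0, C 1.
- Akathisia on double-blind Day 20: A 1, B 1, C 0.

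The first record fails whichever window is chosen. The other two depend on which sentence the programmer follows.

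**The case against.** The strongest reply is that 8.4.6 shows its intent. The 30-day end is introduced as part of the double-blind definition, and the instruction to summarise the periods separately implies that events belong to the period in which they occur. That stands. A reader might infer that the run-in table will count double-blind and follow-up events as run-in events; the text does not establish this. It establishes that the window is contradictory, and reading C is the likely intent.

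A reader might also infer that patch-vehicle safety as a whole is misreported, or that the run-in table was meant as the vehicle or washout reference. The protocol gives it no such role. The randomised placebo arm wears two placebo patches daily for six weeks and is summarised on the SAF. That arm holds only subjects who had already completed at least 3 days of run-in patches, so it does not replace the missing leavers, but it does supply the vehicle comparison.

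Nor are run-in AEs leading to discontinuation zero by construction: an event that starts in run-in and leads to withdrawal after the first double-blind patch can be counted. Only withdrawals before that patch are lost. Section 8.4.6 also promises its SAE and withdrawal tables by treatment arm, so no run-in version of those was undertaken.

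The data themselves are not lost: individual data are listed (8.4) and SAEs are reported within 24 hours (6.2.1.5).

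Finally, 8.4.7 sends table details to the SAP, which was not available for this check. A cut-off date alone would be ordinary SAP content. But the protocol itself fixes the number of sets, ties safety to the SAF and states the run-in rule, so the SAP would have to depart from the protocol to correct the population.

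**Conclusion.** The point holds in limited form. With certainty, from the definitions alone, the promised Screening/Run-in AE summary omits every subject who left before a double-blind patch, and AEs that led to withdrawal before randomisation appear in no summary table. The run-in TEAE window is self-contradictory; a miscount is possible but not certain.

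The number omitted is unknown. The range of 68 to 262 rests on an assumed 10% to 30% loss between the first run-in patch and randomisation, and the documents give no basis for narrowing it or for estimating how many of those subjects left because of an AE.

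The damage is confined to one descriptive summary. The double-blind safety comparison and the efficacy analyses are untouched. It should be corrected because the correction costs little.

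**What to change.** 1. In 8.4.1, add a run-in safety set: all subjects with at least one single-blind patch applied. Use it for the Screening/Run-in summaries of AEs, SAEs and AEs leading to discontinuation, shown overall and split by randomised / not randomised.
2. In 8.4.6, replace the sentence "The same rule applies for Run-in Period" with a definition of its own: a run-in TEAE is an AE that starts or increases in severity from the first single-blind patch up to, but not including, the first double-blind patch; for subjects never randomised, the window runs to the end of their AE follow-up.
3. Keep the SAF for all double-blind summaries.

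The cost is protocol and SAP wording, one extra analysis flag and a slightly longer AE table. No new data are needed, since AEs are already recorded from consent.

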8.4.7 Data to be Analyzed

Data handling will be the responsibility of Quintiles. The data will be inspected for inconsistencies by performing validation checks.

All details regarding the statistical analysis and the preparation of tables, listings and figures will be described in the SAP prepared by Quintiles and approved by the Sponsor before database lock.

The statistical analysis will be performed by Quintiles. After database lock, the final SAS data sets in SDTM and ADaMs formats will be transferred to Noven with SAS programs and all supportive documentation.

8.4.8 Missing Data

MMRM is the best method to control Type I error rate and minimize bias in the presence of missing data, although this does not fully overcome the issues and assumptions are still required to be made regarding the missing data mechanisms. Nevertheless, in the presence of a high dropout rate performance of sensitivity analysis is critical. The purpose of sensitivity analysis is to explore whether different analyses under different sets of missingness assumptions provide robust efficacy results. The sensitivity analysis will be performed on primary endpoints. The extent to which efficacy results are stable across such an analysis provides confidence in the statistical conclusions.

- Missing data can be considered to be missing completely at random (MCAR), missing at random (MAR), or missing not at random (MNAR) according to the National Academy of Sciences (2010). Details are provided in the SAP.

8.5 Subject Disposition and Characteristics

The disposition summary will include all enrolled subjects. Subject characteristics will be obtained at Screening and will be summarized for all subjects. Summaries will include descriptive statistics for continuous variables (sample size, mean, and SD, median, minimum, and maximum) and for categorical variables (sample size, frequency and percent). Subject characteristics may include, but are not limited to: age, gender, race/ethnicity, height, weight, and body mass index.

8.6 Safety

Safety variables will be summarized based on the SAF.

Noven Pharmaceuticals, Inc.
HP-3070-GL-04
HP-3070

74

8.6.1 Adverse Events

The TEAEs are defined as AEs that first occurred or worsened in severity after the first administration of the study drug. Adverse event summaries will include incidence of TEAEs by MedDRA preferred term and system organ class, SAEs (including deaths), AEs that led to study drug discontinuation, AEs by severity, and AEs by relationship to study drug.

8.6.2 Clinical Laboratory Evaluations

Laboratory assessments will be presented as mean changes from Baseline and incidence of abnormal values. Shift tables will be presented for selected parameters. Of special interest are prolactin levels, fasting glucose, and lipids.

8.6.3 Vital Signs Measurements, Physical Findings and Other Safety Evaluations

Descriptive statistics for the change from Baseline will be summarized at each visit for C-SSRS, SAS, BARS, and AIMS.

Mean changes from Baseline and incidence of treatment-emergent abnormal vital signs, weight, and ECG results will be summarized. The number and proportion of subjects with orthostatic hypotension will also be summarized.

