23. Subject has a history of pituitary adenoma or cancer <5 years prior to Screening. Subjects currently being treated for cancer may not be enrolled in the study.
24. Female subject who is breastfeeding.
25. Female subject with a positive urine pregnancy test that is confirmed positive by serum pregnancy test at Screening or Baseline.
26. Subject who currently (within the past 6 months) meets the DSM-5 criteria for substance use disorders (excluding nicotine and caffeine).
27. Subject has positive urine drug/alcohol screen at the Screening Visit. Positive results that are due to short-term prescription medications that can be safely discontinued (e.g., opioids for acute pain that has resolved) may continue at the discretion of the Investigator with the agreement of the Sponsor/designee. Subjects with positive cannabis results may be included, provided the Investigator does not feel the subject is a compliance risk and the subject does not fulfill the criteria for substance abuse or dependence as stated in Exclusion Criterion 26 above, the subject agrees to abstain for the duration of the study, and with the concurrence with the Sponsor/designee.
28. Subject is at imminent risk of self-harm or harm to others, in the Investigator's opinion based on clinical interview and responses provided on the C-SSRS. Note that

Noven Pharmaceuticals, Inc.
HP-3070-GL-04
HP-3070

40

subjects will be excluded if they report suicidal ideation meeting the description of C-SSRS Type 4 or 5 (i.e., suicidal ideation with intent, with or without a plan) in the past 6 months or suicidal behavior (as described by the C-SSRS) in the past 12 months at Screening. Subjects will also be excluded at Baseline if they report suicidal ideation of Type 4 or 5 or suicidal behavior, as measured by the C-SSRS between Screening and Baseline.

29. Subject has a known allergy or hypersensitivity to asenapine.
30. Subject has current or history of allergy or hypersensitivity to adhesive dressings.
31. Subject has history of allergy to more than 2 distinct chemical classes of drug (e.g., sulfas and penicillins).
32. Subject has any skin abnormality present at the potential patch application site that is likely to be aggravated by the study drug (i.e., infection, rash, excessive fragility or dryness, any cut or abrasion), presence of tattoo, excessive hair or open sores, or scar tissue. Presence of significant skin disorder such as atrophy, psoriasis, or vitiligo.

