6.2.5 Suicidality: Columbia-Suicide Severity Rating Scale (C-SSRS)

Suicidality will be monitored during the trial using the C-SSRS.¹³ The C-SSRS facilitates prospective, systematic monitoring for emergence of suicidality within clinical trials and it is a low-burden, clinician-administered tool that covers the wide spectrum of suicidality from ideation to behavior. A training tool will be supplied to the site by the Sponsor for use by staff members that have not had C-SSRS training within the past 2 years. The site will document training of selected staff members and file the training certificates in the trial master file.

This trial will use the “Baseline/Screening” and “Since Last Visit” versions of the scale. The “Baseline/Screening” version, which assesses the lifetime experience of the subject with suicide events and suicidal ideation and the occurrence of suicide events and/or ideation within a specified time period prior to entry into the trial, will be completed for all subjects at the Screening and Baseline visits to determine eligibility (prior to the first dose). Any subject with suicidal ideation within the last 6 months or suicidal behavior within the past 12 months or who in the clinical judgment of the Investigator presents a serious risk of suicide should be excluded from the study. Subjects will also be excluded if they report suicidal ideation or suicidal behavior at Baseline. The “Since Last Visit” C-SSRS form will be completed at all post-Screening visits. A copy of the scale is presented in Appendix 10 (Section 20.0).

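### C-SSRS is to be summarised as change from Baseline, but the protocol defines no C-SSRS score and does not fix which form or recall window is the Baseline reference

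*Protocol*

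**What the plan says.** Two protocol sections prescribe the summary. Section 8.4.6 says: "Scores for C-SSRS, SAS, BARS, and AIMS will be summarized for each treatment arm using descriptive statistics at each visit", and the sentence goes on to ask for both raw and change values: "using descriptive statistics at each visit for raw numbers and change from baseline values". Section 8.6.3 repeats the change part: "Descriptive statistics for the change from Baseline will be summarized at each visit for C-SSRS, SAS, BARS, and AIMS".

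Section 6.2.5 describes two versions of the instrument.

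- **Baseline/Screening form.** It is the one "which assesses the lifetime experience of the subject with suicide events and suicidal ideation", and it also covers "the occurrence of suicide events and/or ideation within a specified time period prior to entry into the trial". It "will be completed for all subjects at the Screening and Baseline visits to determine eligibility".
- **Since Last Visit form.** The "C-SSRS form will be completed at all post-Screening visits".

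The Baseline/Screening form in Appendix 10 has a lifetime column and a second column headed in years, with the number left blank. Table 1 schedules C-SSRS at Screening, at Baseline and at each weekly visit of the treatment period.

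**The concern.** A change from Baseline needs one defined quantity, measured the same way at both ends. Neither condition is met here.

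First, sections 6.2.4.1 to 6.2.4.3 define a total, movement or global score for SAS, AIMS and BARS. Section 6.2.5 defines nothing comparable for C-SSRS. The behavior pages in Appendix 10 hold Yes/No items, counts of attempts and lethality codes. (The ideation items were not in the text available to me, and I rest nothing on them.)

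Second, the Baseline visit falls under both form instructions, and no sentence says which form or column gives the Baseline value. If the Baseline/Screening form is used, a lifetime or multi-year answer is compared with an answer covering about one week.

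C-SSRS results are a listed safety endpoint in acutely ill patients, a third of whom receive placebo. The question of interest is how many subjects in each arm have ideation or behavior after treatment starts. A change across unequal recall windows does not answer it.

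**Working it through.** The protocol gives no figure for this summary, so there is nothing to reproduce. The check sets out what the change would be under each reference that the wording allows.

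**Inputs**

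- Subjects per arm: 204 (section 8.1).
- Proportion with lifetime suicidal behavior, L: assumed 25%, range 10% to 40%. The protocol gives no rate.
- Proportion with new behavior at a post-baseline visit, w: assumed 2%, doubled to 4% in an arm with a true excess.
- Eligibility: exclusion criterion 28 removes subjects with suicidal behavior in the 12 months before Screening or between Screening and Baseline. On ideation, "subjects will be excluded if they report suicidal ideation meeting the description of C-SSRS Type 4 or 5" in the past 6 months. Behavior more than 12 months old is not a listed exclusion.

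**Reference A: lifetime column of the Baseline/Screening form**

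Change in proportion positive = w - L.

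| L | w = 2% | w = 4% | Difference between arms |
|---|---|---|---|
| 10% | 0.02 - 0.10 = -0.08 | 0.04 - 0.10 = -0.06 | 0.02 |
| 25% | 0.02 - 0.25 = -0.23 | 0.04 - 0.25 = -0.21 | 0.02 |
| 40% | 0.02 - 0.40 = -0.38 | 0.04 - 0.40 = -0.36 | 0.02 |

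At L = 25%, 0.25 × 204 = 51 subjects per arm are positive at Baseline. At a later visit about 0.02 × 204 = 4 are positive, or 0.04 × 204 = 8 in the arm with the excess. Both arms look improved, although the second has twice as many events.

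For one subject, scored 1 for yes and 0 for no:

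- remote history, no new event: 0 - 1 = -1, an apparent improvement;
- remote history, new event: 1 - 1 = 0, no change;
- no history, new event: 1 - 0 = +1.

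If new events are independent of history, a share L of them (10% to 40%) registers as no change. If they all occur in subjects with a history, all of them do.

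**Reference B: Since Last Visit form at the Baseline visit**

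Criterion 28 bars behavior between Screening and Baseline, so the Baseline proportion for behavior is 0 by design. The changes are 0.02 - 0 = +0.02 and 0.04 - 0 = +0.04. The excess shows as a rise, and the difference between arms is again 0.02.

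**Reference C: the limited pre-entry column**

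Its length is not stated. If it is 12 months or less, criterion 28 again makes the Baseline proportion for behavior 0. If it is longer, the result lies between B and A.

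The same data can therefore give -0.23 or +0.02 in an arm, depending on a choice that the protocol does not make.

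**The case against.** The strongest reply is that the lifetime reference is only one possibility. No sentence makes the lifetime column the Baseline value. Section 6.2.5 as worded also places the Since Last Visit form at Baseline, so a reference with a matching window may already be collected, and with it the artificial shift in behavior disappears. A reader might infer that every arm must show a false improvement and that emergent suicidality would be hidden. The protocol does not support that, for three reasons:

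- the shift depends on an unspecified choice of reference and on an assumed history rate;
- whatever shift arises is shared by randomised arms on average, so the contrast between them is kept;
- section 8.4.6 also requires raw values by arm and visit (4 against 8 subjects in the illustration), and new or worse psychiatric symptoms and serious events are recorded and tabulated as AEs and SAEs.

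It is also fair that section 8.6.3 does not say mean change for C-SSRS, that section 8.4 puts categorical variables in frequency tables, that all safety output is descriptive without tests, and that the SAP, which I have not seen, may set out the tables.

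All of this limits the point but does not remove it. A frequency table of change across unequal windows has the same flaw as a mean. Raw counts visit by visit do not give the number of subjects with any post-baseline event. The AE route counts symptoms of other psychiatric disorders only when they are new or exceed what the medical history records, so a recurrence at the former level may be missed. And the protocol does not leave the summary open: it prescribes change from Baseline twice.

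**Conclusion.** The point holds in a limited form. Sections 8.4.6 and 8.6.3 prescribe a summary that does not suit the instrument, and section 6.2.5 leaves its reference value ambiguous. If the Baseline/Screening form supplies that value, the result is hard to interpret. On its lifetime column all arms drift toward apparent improvement, by 0.08 to 0.38 in proportion positive for 10% to 40% lifetime history and 2% behavior per visit, and a new event in a subject with a history shows as no change. These rates are assumptions; with no lifetime history there is no drift.

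Emergent suicidality would be obscured in this one summary, not concealed across the safety output, and the comparison between arms would not be biased on average. The efficacy conclusions are not affected.

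**What to change.** 1. Remove C-SSRS from the change-from-Baseline sentences in sections 8.4.6 and 8.6.3.
2. In their place, report by arm the number and percentage of subjects with any post-baseline suicidal ideation, by type, and with any post-baseline suicidal behavior.
3. Add a shift table of the worst post-baseline category against one named pre-treatment reference with a matching window. The Since Last Visit form at the Baseline visit is the natural choice and, on the present wording of section 6.2.5, is already collected.
4. Show lifetime history only as a baseline characteristic.
5. Reconcile the two form instructions for the Baseline visit in section 6.2.5, so that it is clear which form or forms are completed there and for what purpose.

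This brings C-SSRS into line with section 8.6.2, which plans incidence and shift tables for laboratory data, and with the incidence of treatment-emergent abnormalities that section 8.6.3 plans for vital signs, weight and ECG. The cost is a few sentences of protocol text and a different table shell. No new data are needed, provided that sites complete the Since Last Visit form at Baseline.
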